## **14.0 PROTECTION OF HUMAN SUBJECTS**

### **14.1 Serious Adverse Event (SAE) Reporting**

An adverse event or suspected adverse reaction is considered “serious” if, in the view of either the investigator or the sponsor, it results in any of the following outcomes:

- Death
- A life-threatening adverse drug experience – any adverse experience that places the patient, in the view of the initial reporter, at immediate risk of death from the adverse experience as it occurred. It does not include an adverse experience that, had it occurred in a more severe form, might have caused death.
- Inpatient hospitalization or prolongation of existing hospitalization
- A persistent or significant incapacity or substantial disruption of the ability to conduct normal life functions.
- A congenital anomaly/birth defect.

Important medical events that may not result in death, be life-threatening, or require hospitalization may be considered a serious adverse drug experience when, based upon appropriate medical judgment, they may jeopardize the patient or subject and may require medical or surgical intervention to prevent one of the outcomes listed in this definition. Examples of such medical events include allergic bronchospasm requiring intensive treatment in an emergency room or at home, blood dyscrasias or convulsions that do not result in inpatient hospitalization, or the development of drug dependency or drug abuse (21 CFR 312.32).

- Important medical events as defined above, may also be considered serious adverse events. Any important medical event can and should be reported as an SAE if deemed appropriate by the Principal Investigator or the IND Sponsor, IND Office.
- All events occurring during the conduct of a protocol and meeting the definition of a SAE must be reported to the IRB in accordance with the timeframes and procedures outlined in “The University of Texas M. D. Anderson Cancer Center Institutional Review Board Policy for Investigators on Reporting Unanticipated Adverse Events for Drugs and Devices”. Unless stated otherwise in the protocol, all SAEs, expected or unexpected, must be reported to the IND Office, regardless of attribution (within 5 working days of knowledge of the event).
- All life-threatening or fatal events, that are unexpected, and related to the study drug, must have a written report submitted within 24 hours (next working day) of knowledge of the event to the Safety Project Manager in the IND Office.
- Unless otherwise noted, the electronic SAE application (eSAE) will be Utilized for safety reporting to the IND Office and MDACC IRB.

- Serious adverse events will be captured from the time of the first protocol-specific intervention, until 30 days after the last dose of drug, unless the participant withdraws consent. Serious adverse events must be followed until clinical recovery is complete and laboratory tests have returned to baseline, progression of the event has stabilized, or there has been acceptable resolution of the event.
- Additionally, any serious adverse events that occur after the 30 day time period that are related to the study treatment must be reported to the IND office. This may include the development of a secondary malignancy.

**Reporting to FDA:**

- Serious adverse events will be forwarded to FDA by the IND Sponsor (Safety Project Manager IND Office) according to 21 CFR 312.32.

It is the responsibility of the PI and the research team to ensure serious adverse events are reported according to the Code of Federal Regulations, Good Clinical Practices, the protocol guidelines, the sponsor's guidelines, and Institutional Review Board policy.

**Investigator Communication with Supporting Companies:**

Serious adverse events (SAE) will be captured from the time of the first protocol-specific intervention, until 30 days after the last dose of drug. The investigator will inform Incyte of any SAE or pregnancy within 24 hours of being aware of the event via email and/or fax. Respective companies will be informed based on the attribution of a given event:

1. Due to RUXOLITINIB alone – These SAEs will only be reported to INCYTE.
2. Due to both the RUXOLITINIB and decitabine – These SAEs will be reported to INCYTE
3. All pregnancies will be reported to INCYTE If the investigator can't associate causality with one or the other alone then causality needs to be associated with the combination of the products. These SAEs will go to INCYTE.

Adverse events will be documented in the Leukemia-specific AE Recording and Reporting Guidelines attached in Appendix E. medical record and entered into the case report form. PDMS/ CORE will be used as the electronic case report form for this protocol. All adverse events will be captured in CRF during Phase I portion of the study. In Phase II, only Grade 3 and higher related will be captured in the CRF. Investigator or physician designee is responsible for verifying and providing source documentation for all adverse events and assigning the attribution for each event for all subjects enrolled on the trial. SAEs must be documented using the MDACC IND eSAE electronic form. This form must be completed and supplied to Incyte within 24-hours/1-business day at the latest on the following working day. The initial report must be as complete as possible, including details of the current illness and (serious) adverse event, and an assessment of the causal relationship between the event and the investigational product(s). Information not available at the time of the initial report (e.g., an end date for the adverse event or laboratory values received after the report) must be documented on a follow-up MDACC IND eSAE reporting form.

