	Febrile neutropenia (ANC < 1.0 x 10  /L, fever ≥ 38.5°C)	Interrupt study treatment dosing until fever resolved and ANC ≤ grade 2, then restart study treatment at reduced level as per Table 5

Worst Toxicity CTCAE Grade* unless otherwise specified (Value)		Dose Modification Guidelines At any time during a cycle of therapy (including intended day of dosing)
Anemia# only requires dose reductions after cycle 6	Doubling of transfusion frequency from baseline or hemoglobin	Hold Ruxolitinib only and continue Decitabine, if hemoglobin (or transfusion frequency) returns to baseline within 28 days restart Ruxolitinib at same dose, if this recurs again then reduce dose as per Table 5
NON-HEMATOLOGICAL TOXICITIES		
GASTROINTESTINAL		
Diarrhea	Grade 2 (4-6 stools/day over baseline, etc) despite the use of optimal antidiarrheal medications	Hold Ruxolitinib dosing until resolved to $\leq$ grade 1, or baseline, then restart at unchanged dose level
	Grade 3 ( $\geq$ 7 stools/day over baseline, etc) despite the use of optimal antidiarrheal medications	Hold Ruxolitinib dosing until resolved to $\leq$ grade 1, or baseline, then restart study treatment at reduced level as per Table 5
	Grade 4 (life-threatening consequences, hemodynamic collapse, etc) despite the use of optimal antidiarrheal medications	Permanently discontinue study treatment dosing
Vomiting/Nausea***	Grade 1 & 2 not requiring treatment or controlled using standard anti-emetics	Maintain dose level
	Grade 3 or 4 vomiting or Grade 3 nausea that cannot be controlled despite the use of standard anti-emetics	Interrupt study treatment dosing until resolved to $\leq$ grade 1, or baseline, then restart study treatment at reduced level as per Table 5
HEPATIC		
Total Bilirubin	Grade 3 or 4	Interrupt study treatment dosing until resolved to $\leq$ grade 2, or baseline, then restart study treatment at reduced level as per Table 5

Worst Toxicity CTCAE Grade* unless otherwise specified (Value)	Dose Modification Guidelines At any time during a cycle of therapy (including intended day of dosing)

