## 9.0 EVALUATION DURING TREATMENT/INTERVENTION

### Response assessment

Response assessment (RA) can be performed at the end of any cycle after cycle 1. Specific events that will prompt response assessment include of resolution of splenomegaly on exam and clearance of blasts from the peripheral blood, which will prompt bone marrow aspirate and biopsy. Patients continuing to maintain at least SD by the response criteria shown below should continue to receive ruxolitinib and decitabine until progression of disease, unacceptable toxicity or patient withdrawal. Patients may receive up to 24 cycles in this study. Patients may proceed to allogeneic stem cell transplant at any time after Cycle 1. Dose modification of ruxolitinib will be allowed after Cycle 1. RUXOLITINIB will be provided by the sponsor for a maximum of up to 2 years, after which it will be required to procure it from commercial sources.

Adverse events will be captured as long as patients are on study and will be used to fully characterize the tolerability and toxicity of this combination therapy. These events will be defined based on the NCI CTCAE version 4. Patients who withdraw from the study for any reason will be followed and seen 28 days (+/- 5 days) for an end of study visit to capture all adverse events.

Adverse events will only be captured after the first dose of RUXOLITINIB has been administered.

**Table 3** - Schedule of study procedures

Evaluation	Baseline screening	Cycle 1	Cycle 2 and beyond	Response assessment	End of Study
		At least once weekly (+/- 3 days)	At least once every 2 weeks (+/- 3 days)		(+/- 5 days)
History	x				
physical exam	x	x	x		x
Vital signs	x	x	x		x
Concomitant medications 	x	x	x		x
Adverse event assessment		x	x		x
HIV, HBV, HCV serology	x				
MUGA or Echo	x				
ECG	x				x
CT/MRI abd/pelvis without contrast,	x			x 	

if clinically indicated					
Pregnancy test	X				
CBC with differential	X	X	X		X
Chemistry 	X	X	X		X
Bone marrow biopsy	X			X 	X
Bone marrow aspirate	X			X 	X
Jak2/MPL allele burden 	X				
Correlative studies 	X				X
Chest X-ray	X				

1. Preferentially performed on the marrow, but will be performed on the peripheral blood if a specimen cannot be obtained. Allele burden will not be repeated if neither Jak2 nor MPL is mutated. The sample will be obtained in 5 ml EDTA tube.

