### Analysis method

Data analysis will be performed using SAS or S-plus, as appropriate. All patients who received at least 1 dose of the combined agents will be included in the intent-to-treat analysis for efficacy. Demographic and disease characteristics of the patients at registration will be summarized using descriptive statistics such as mean, standard deviation (SD), median and range. Overall response rates will be presented with 95% confidence intervals.

The association between response and patient and disease characteristics will be examined by two-sample t-test (or Wilcoxon rank-sum test) or Chi-square test.

The data from all patients who received the combined therapy during the study will be included for safety analysis. Safety data will include laboratory, physical exam, and adverse event reports on study patients. These descriptive summaries will be provided for all patients for each safety parameter by cycle, grade, and relationship to treatment.

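### The phase II CRF, limited to related grade 3 or higher adverse events, cannot support the adverse event summary by grade and relationship that Section 13 promises for all patients.

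*Combined protocol and SAP*

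**What the plan says.** Section 14, under Investigator Communication with Supporting Companies, sets two capture rules. For phase I: "All adverse events will be captured in CRF during Phase I portion of the study". For phase II: "In Phase II, only Grade 3 and higher related will be captured in the CRF". It then adds a duty that does not depend on phase, grade or relationship: "Investigator or physician designee is responsible for verifying and providing source documentation for all adverse events and assigning the attribution for each event".

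Section 13, Analysis method, makes no such distinction. On the population: "The data from all patients who received the combined therapy during the study will be included for safety analysis". On content: "Safety data will include laboratory, physical exam, and adverse event reports on study patients". On presentation: "These descriptive summaries will be provided for all patients for each safety parameter by cycle, grade, and relationship to treatment".

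Section 9, Response assessment, gives the purpose: "Adverse events will be captured as long as patients are on study and will be used to fully characterize the tolerability and toxicity". It sets no limit by grade or relationship, and it does not say whether capture means the CRF or the source record.

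**The concern.** The analysis section promises a breakdown that the data collection rule does not feed. In phase II an event enters the CRF only if it passes two tests, grade and relatedness. These are two of the three variables by which the summary is to be broken down.

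The second test is a judgement made before data entry. The trial is single-arm, and Section 10 expects myelosuppression from both drugs and a risk of infection. Section 8.1 recognises that treatment and disease can be hard to separate, since it asks for a marrow examination to tell the cause of prolonged cytopenia. When relatedness decides whether an event is entered, instead of being recorded as a field, a user of the database cannot test how far the safety picture depends on attribution.

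At stake are a coherent adverse event table for the dose carried into phase II and a fair comparison of the two phases.

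**Working it through.** **1. Patients affected.** Inputs: up to 12 in phase I and up to 24 in phase II (Section 6, and Number of patients in Section 8); a phase I maximum of 18 evaluable patients (Section 13, Basis for sample size).

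- Sections 6 and 8: 12 + 24 = 36, which reproduces the stated maximum. Phase II share: 24/36 = 66.7%.
- Section 13 phase I maximum: 18 + 24 = 42. Phase II share: 24/42 = 57.1%.

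The 24 is a ceiling. Table 9 gives average phase II sizes from 7 to 22, depending on the true response and toxicity rates.

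**2. What each CRF can hold.** Cross-classify events by the two variables that Section 13 names.

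| Event | Phase I CRF | Phase II CRF | Other phase II record |
|---|---|---|---|
| Grade 3 or higher, related | yes | yes | source; eSAE if serious |
| Grade 3 or higher, unrelated, serious | yes | no | source and eSAE |
| Grade 3 or higher, unrelated, not serious | yes | no | source only |
| Grade 1-2, related | yes | no | source; eSAE if serious |
| Grade 1-2, unrelated | yes | no | source; eSAE if serious |

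In the two-by-two layout of grade (1-2, or 3 and above) by relationship (related or not), phase I can fill four cells and phase II one. A phase II table by relationship therefore has one category, and a table by grade begins at grade 3.

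**3. Effect of pooling.** Section 13 defines one safety population and does not separate the phases. Take an adverse event type that the phase II rule excludes, for example grade 1-2 events of one kind. Assume, for illustration, full enrolment and the same true proportion of patients, p, in both phases. Then

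pooled proportion shown = (p × N1 + 0 × N2) / (N1 + N2).

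- N1 = 12, N2 = 24: 12p/36 = 0.33p.
- N1 = 18, N2 = 24: 18p/42 = 0.43p.

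The pooled table would show about a third to two fifths of the true figure, and a side-by-side table would show p against zero. The difference comes from the capture rule alone.

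**4. Events that change treatment.** Table 2 provides for holding ruxolitinib at "Grade 2 (4-6 stools/day over baseline, etc) despite the use of optimal antidiarrheal medications". Table 2 applies to toxicity judged clearly related to ruxolitinib, so this event passes the relatedness test. It fails the grade test and would not be entered as an adverse event in the phase II CRF.

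**5. What is unaffected.** Table 3 schedules physical examination, vital signs, CBC and chemistry for every patient, at least weekly in cycle 1 and at least every two weeks afterwards. Cytopenias therefore show in the laboratory data whatever their attribution. Section 14.1 requires all SAEs to go to the IND Office regardless of attribution.

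**The case against.** The strongest reply is that the restriction concerns data entry, not observation. Section 13 counts laboratory and examination results as safety data, and these are complete. Related grade 3 or higher events can be tabulated by cycle and grade. Death or inpatient hospitalization makes an event serious, so a severe infection put down to leukemia would often reach eSAE. Every event, with its attribution, must be documented in source for all subjects. Tolerability is the phase I objective, and there every event is captured; the phase II primary outcome is response. The inconsistency could be removed by narrowing Section 13 alone. Finally, Sections 10 and 14 refer to Appendix E for recording guidelines, and that appendix is not in the text reviewed.

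Most of this stands, and it rules out two stronger readings. A reader might infer that no safety analysis is possible for the phase II patients. The documents do not support that, because only part of the adverse event table fails. A reader might also infer that the missing events are lost for good. Section 14 keeps them in source, so they can be recovered, but only by abstracting charts.

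Three things survive. Section 13 has no phase II exception, so the two sections conflict as written. Non-serious unrelated events of grade 3 or higher are in neither the CRF nor eSAE. Narrowing Section 13 alone would make the text consistent but would leave attribution deciding which severe events enter the CRF. Acceptable toxicity is also a stated condition in Section 13 for taking the regimen further, so phase II safety is not a side issue.

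**Conclusion.** The concern holds as a conflict between the collection rule and the promised summary. Followed as written, the plan cannot produce from the phase II CRF the adverse event summary by grade and relationship for up to 24 patients (67% of 36, or 57% of 42), and a pooled table would mix two capture rules. The mismatch with Section 9 is softer, because that section does not name the CRF, but its aim of full characterization is not served.

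This rests on reading the Section 14 sentence literally and on Appendix E not overriding it.

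Two further inferences go beyond the documents. One is a figure for how far severe infection or bleeding would be under-reported: the plan gives neither event rates nor the share attributed to disease, so any such number would be invented. The other is that toxicity stopping is weakened. Section 13 defines monitored toxicity by grade, with no relatedness condition, but the documents do not say whether monitoring runs from the CRF. That should be clarified; it is not shown to be a defect.

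**What to change.** - **Section 14.** Have the phase II CRF capture all events of grade 3 or higher whatever their attribution, with attribution as a recorded field, plus events of any grade that lead to a hold, reduction or discontinuation. Reconcile SAEs and deaths from eSAE into the safety dataset.
- **Section 13, Analysis method.** Limit the phase II adverse event summary to what is captured, and present phase I and phase II separately.
- **Section 9.** Align the statement of purpose with the two capture rules.

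The cost is a few sentences of protocol, a revised CRF completion guideline, and some extra data entry for up to 24 patients from attributions already made in source. The reported grade 3 or higher event rate will be higher. Most grade 1-2 events would still not be entered, which is acceptable once Section 13 says so. The change is cheapest before phase II data entry begins; afterwards it means going back to the charts.

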**15.0 CORRELATIVE STUDIES**

After one cycle of therapy, after 3 cycles, and then every 3 cycles while on the study (in addition to baseline and end of study samples), peripheral blood will be collected for measurements of inflammatory cytokine levels, (including but not limited to IL6, TNF-alpha, CRP and IL10), expression of different proteins related to intracellular signaling, (including but not limited to STAT3, STAT5, and JAK2), and methylation of genes (including but not limited to p15, ER, and ECAD). This will include collection of: one red top (10ml) and two purple top tubes (10ml each). All samples will be submitted to the laboratory of [name] at MD Anderson.

All research samples may not be drawn at all times, missed samples will not be considered a deviation.

#### 16.0 CONCOMITANT MEDICATIONS

The use of standard agents deemed necessary for patient supportive care are permitted (antibiotics, allopurinol, GCSF). Only other chemotherapy agents or investigational agents are prohibited. Temporary prior measures to control blood counts, such as apheresis or hydrea are allowed.

